7.2.4. Vital Signs

Vital signs including blood pressure, heart rate, temperature, and respiratory rate will be documented for subjects during study as outlined in Table 1.

7.2.5. Laboratory Measurements

Laboratory safety parameters will be analyzed as clinically indicated, using standard validated methods. Parameters to be assessed will be at the discretion of the investigator.

The following parameters may be assessed by the laboratory as described in Table 1:

- Hematology: hemoglobin, hematocrit, erythrocytes, erythrocyte mean corpuscular volume, leukocytes, mean corpuscular hemoglobin, mean corpuscular hemoglobin concentration, neutrophils, lymphocytes, monocytes, eosinophils, basophils and platelets
- Blood Biochemistry: albumin (ALB), alkaline phosphatase (AP), alanine aminotransferase (ALT; SGPT), aspartate aminotransferase (AST; SGOT), bicarbonate, blood urea nitrogen (BUN), calcium (Ca), chloride (Cl), creatinine, creatine kinase, gamma-glutamyl transferase (GGT), globulin, glucose, lactate dehydrogenase (LDH), phosphorus, potassium (K), sodium (Na), total bilirubin, direct bilirubin, total cholesterol, total protein, triglycerides, uric acid.
- Urine or serum pregnancy test: Pregnancy testing will be performed in female subjects of childbearing potential.

The investigator will receive the laboratory report from the central laboratory. After reviewing the report and evaluating any results that are outside the normal range, the investigator must sign and date the laboratory report.

Tests resulting in abnormal laboratory values that have been classified by the investigator as abnormal, clinically significant should be repeated as soon as possible after receiving the laboratory report to rule out laboratory errors.

Any deviation outside of the reference range considered by the investigator as clinically significant (ie, classified as an abnormal, clinically significant value) at any visit will be documented in the CRF as an AE (Section 9).

7.2.6. Plasma Sample for Concomitant Antiepileptic Drug(s)

Plasma samples to ensure that concomitant AEDs dosing is within an acceptable range will be conducted during the study when clinically indicated, as outlined in Table 1.

7.2.7. Electrocardiograms

Twelve-lead ECGs will be conducted as clinically indicated after the subject has been in the supine position resting for ≥ 5 minutes. Heart rate, PR duration, QRS duration, QT duration,

Confidential Page 54 of 105

22 September 2022

QTcF (Fridericia's correction formula), and the investigator's overall interpretation will be recorded.

7.2.8. Doppler Echocardiography

Doppler echocardiography will be conducted at a facility with experience for the subject's age during study as outlined in Table 1. Doppler echocardiography uses ultrasound technology to examine the heart or blood vessels. An ECHO uses high frequency sound waves to create an image of the heart while the use of Doppler technology allows determination of the speed and direction of blood flow by utilizing the Doppler effect. A manual of proper ECHO technique for sites is provided in a separate document.

7.2.9. Chest X-ray (France and Netherlands only)

For subjects enrolled in France and Netherlands only, an anterior/posterior chest x-ray will be obtained as clinically indicated.

7.2.10. Electroencephalogram (EEG) (Italy only)

Routine electroencephalogram (r-EEG) will be obtained as clinically indicated at centers in Italy only. The potential for EEG to induce seizures should be considered and if a patient is determined to be at high risk for EEG-induced seizure, then EEG should not be conducted. Standard clinical measures should be in place to mitigate against EEG-induced seizure. As these EEGs are considered exploratory, they should be locally read and stored in the site files. EEG recordings will not be captured in the CRF.

7.2.11. Columbia-Suicide Severity Rating Scale

The Columbia-Suicide Severity Rating Scale (Appendix 2) will be assessed during study as outlined in Table 1. The C-SSRS is a validated rating scale that assesses suicidal behavior and ideation. The scale is used to assess and track suicide events and provides a summary measure of suicidal tendency. The C-SSRS version 1/14/19 (Since Last Visit) will be used in this study as appropriate for the age and level of intellectual development.

Subjects who are younger than 7 years chronologically, or who are judged by the investigator not to have the mental capacity to understand the questions as specified on the C-SSRS, will not complete the rating. The investigator should use his/her judgment to substitute intellectually-appropriate questions to probe the tendency for self-harm.

If a subject with the intellectual capacity to complete the C-SSRS has their 7th birthday during the study, use of the C-SSRS should be initiated at subsequent visits.

7.2.12 Adverse Events

Adverse events will be collected from the time of signing the informed consent form/assent form until the end of the study, including the follow-up clinic visit. For subjects who participated in 1 of the core studies, adverse events that occur after signing informed consent for this study, but before Visit 1 will be recorded as adverse events in the core study and medical history in ZX008-1900.

Confidential Page 55 of 105

and procedures for the reporting of Ab.

and according to the criteria specified in Section 8.2.
Action period for AE reporting is specified in
Asist at the study site, the study personned will specifically
ave occurred since the last study site visit. All AEs will be
a page.

Acress of Weasurements

Assessed are standard tests or procedures that are commonly used in studies.

Confidential Page 56 of 105

22 September 2022

8. ADVERSE EVENTS

8.1. **Definitions**

8.1.1. Adverse Events

According to ICH guidelines, an AE is any untoward medical occurrence in a patient or clinical investigation subject administered a pharmaceutical product and which does not necessarily have a causal relationship with this treatment. An AE can, therefore, be any unfavorable and unintended sign (including an abnormal, clinically significant laboratory finding), symptom, or disease temporally associated with the use of a medicinal (investigational) product, whether or not considered related to the medicinal (investigational) product. The period of observation for adverse events extends from Visit 1 of ZX008-1900 until the end of study. Adverse events that occur after signing informed consent for this study, but before Visit 1 will be recorded as adverse events in the core study and medical history in ZX008-1900.

Adverse events may include:

- Illness present before core study entry should be recorded in the medical history section
 of the CRF along with any ongoing AEs that were present at the last visit of the core
 study. These events should only be reported as an AE if there is an increase in the
 frequency or severity of the condition from the core study
- Exacerbation of seizures is considered an AE if there was an increase in frequency beyond the subject's typical pre-core study fluctuations, or in the event that seizures lengthen in duration in a clinically meaningful way compared with core study baseline, or if a new seizure type emerges
- A clinical event occurring after consent but before IMP administration
- Intercurrent illnesses with an onset after administration of IMP

Adverse events do not include:

- Medical or surgical procedures (the condition that leads to the procedure is the AE, eg, tonsillitis is the AE if a tonsillectomy is performed)
- Situations where an untoward medical occurrence has not taken place. For example:
 - o Planned hospitalizations due to pre-existing conditions, which have not worsened
 - Hospitalizations that occur for procedures not due to an AE (eg, cosmetic surgery)
 - o Hospitalizations for a diagnostic procedure where the hospital stay is less than 24 hours in duration or for normal management procedures (eg, chemotherapy)

For laboratory safety parameters, any instances of absolute values being outside the reference range or changes at any visit after study start that are considered by the investigator as clinically significant must be recorded in the CRF as AEs. In addition, at the investigator's discretion, any changes or trends over time in laboratory parameters can be recorded in the CRF as AEs if such changes or trends are considered to be clinically relevant, even if the absolute values are within the reference range.

Confidential Page 57 of 105

22 September 2022

Laboratory findings do not need to be reported as AEs in the following cases:

- 1. Laboratory parameters are already beyond the reference range, unless a further increase/decrease can be considered an exacerbation of a pre-existing condition.
- 2. Abnormal laboratory parameters caused by mechanical or physical influences on the blood sample (eg, hemolysis) and flagged as such by the laboratory in the laboratory report.
- 3. Abnormal parameters that are obviously biologically implausible (eg, values that are incompatible with life).
- 4. An abnormal laboratory value that cannot be confirmed after a repeated analysis, preferably in the same laboratory (eg, the previous result could be marked as not valid and should not necessarily be reported as an AE).

8.1.2. Serious Adverse Events

A serious adverse event (SAE) is defined as any untoward medical occurrence that at any dose:

- 1. **Results in death** The event must be the cause of death for the SAE to meet this serious criterion.
- 2. **Is life-threatening** The term "life-threatening" refers to an event in which the subject was at risk of death at the time of the event; it does not refer to an event that hypothetically might have caused death if it had been more severe.
- 3. Requires in-patient hospitalization or prolongation of existing hospitalization The Sponsor considers "hospitalization or prolongation of existing hospitalization" for at least 24 hours as the defining criterion for an SAE. Hospital admissions for planned surgery or for normal disease management procedures (eg, chemotherapy) are not considered as defining criteria for SAEs.
- 4. Results in persistent or significant disability or incapacity.
- 5. Is a congenital anomaly or birth defect?
- 6. **Is medically significant** A medically significant event is defined as an event that does not meet any of the other 5 SAE criteria, but which is judged by a physician to potentially jeopardize the subject or require medical or surgical intervention to prevent 1 of the above outcomes listed as an SAE criterion. Anaphylaxis that is successfully treated by administration of epinephrine prior to other sequelae is an example of a potentially medically important event.

The most important term should be selected as the criteria for the SAE. Medically significant should be used when none of the other terms apply.

Suspected Unexpected Serious Adverse Reactions (SUSARs) are defined as SAEs that do not meet determination of expectedness as determined in accordance with applicable product information (Investigator's Brochure or other reference documentation). Upon receipt of a SAE report from an investigator site, all suspected adverse reactions related to the IMP which occur within the clinical trial will be assessed for expectedness. Any SAE not listed in the reference documentation is considered a Suspected Unexpected Serious Adverse Reaction (SUSAR).

Confidential Page 58 of 105

22 September 2022

SUSARs will be reported by the Sponsor, or its designee, in compliance with local legal requirements. During the course of the study, the Sponsor will report within required timelines all SAEs that are both unexpected and at least reasonably related to the IMP (SUSARs) to the Health Authorities, IECs / IRBs as appropriate and to the Investigators. This study will comply with all applicable regulatory requirements and adhere to the full requirements of ICH Topic E2A (Clinical Safety Data Management: Definitions and Standards for Expedited Reporting [1994]).

For the purpose of data collection in this study, a prolonged seizure or series of seizures from which the subject does not regain consciousness between ictal events, that is at least 30 minutes in duration, is termed status epilepticus (SE). A single episode of SE in a 24-hour period, regardless of whether rescue medication was administered, should be entered in the AE log. If 2 or more episodes occur within 24 hours, each lasting 30 minutes or more, an SAE of SE should be recorded. Hospitalization to manage SE, regardless of the number of episodes, should be reported as an SAE.

Adverse events that do not fall into the above categories are defined as nonserious AEs.

8.2. Severity of Adverse Events

The severity of AEs (whether nonserious or serious AEs) is to be assessed by the investigator as follows (Table 7).

Table 7. Severity Definition of Adverse Event	Table 7.	Severity	Definition	of Adve	rse Events	a
--	----------	----------	-------------------	---------	------------	---

Severity	Definition
Mild	A type of AE that is usually transient and may require only minimal treatment or therapeutic intervention. The event does not generally interfere with usual activities of daily living.
Moderate	A type of AE that is usually alleviated with additional specific therapeutic intervention. The event interferes with usual activities of daily living, causing discomfort but poses no significant or permanent risk of harm to the research participant.
Severe	A type of AE that interrupts usual activities of daily living, or significantly affects clinical status, or may require intensive therapeutic intervention.

^a Clinical Data Interchange Standards Consortium Study Data Tabulation Model Severity Intensity Scale for Adverse Event Terminology

8.3. Causality of Adverse Events

The causal relationship of an AE to IMP must always be assessed by the investigator. All AEs will be classified as either related or not related to IMP. If a causality assessment is not provided for an AE (including an SAE), that AE will be considered as related to IMP.

The degree of certainty with which an AE is attributed to IMP or an alternative cause (eg, natural history of the underlying disease, concomitant medication) will be determined by how well the event can be understood in terms of:

- Known pharmacology of ZX008
- Clinically and/or pathophysiologically plausible context

Confidential Page 59 of 105

22 September 2022

- Reaction of a similar nature previously observed with similar products, or reported in the literature for similar products as being product related (eg, headache, facial flushing, pallor)
- Plausibility supported by the temporal relationship (eg, the event being related by time to administration or termination of treatment with IMP drug withdrawal or reproduced on rechallenge)

The following classifications should be used in categorization of relatedness:

- 1. Not Related: Concomitant illness, accident or event with no reasonable association with study drug.
- 2. Related: The event follows a reasonable temporal sequence from administration of study drug and is definitive pharmacologically; cannot to be attributed to concurrent disease or other factors or medications. A clinically reasonable response should be observed if the study drug is withdrawn or dose reduced.

8.4. Observation Period for Adverse Event Reporting

The observation period for AE and SAE reporting will start at Visit 1 of ZX008-1900 and finish 15 days after the last dose of study drug or the last visit, whichever is later. For subjects who enroll in the open-label extension study from 1 of the core studies, ongoing AEs from the core studies will be considered medical history unless there is an increase in the frequency or severity of the condition from the core study.

If the investigator becomes aware of an SAE that has started after the observation period has finished, and the event could in some way be associated with IMP (irrespective of whether or not it is considered by the investigator to be causally related to IMP), then this must also be reported to the Sponsor (see Section 8.6).

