6.3. Cardiac Follow Up Visit (Clinic Visit 9; last dose + 6 Months)

If the subject completes the study (or discontinues from the study early), and is not switching to commercially available drug, the subject will visit the clinic 6 months after the last dose. At the 6 month follow up visit, the following procedures will be performed, with additional follow-ups based on country of residence (see table 5).

- Abbreviated physical/neurological examination. A full physical and/or neurological examination may be performed, if warranted. Abnormal clinically significant findings must be reported as adverse events.
- 12-lead ECG (conducted and read locally)
- Doppler ECHO
- Record AEs
- Record concomitant medications

If the subject completes the study or discontinues from the study early, the subject will return to the clinic for follow-up cardiac testing (ECHO, ECG, and in some cases, physical examination). The timing and frequency of exams are in Table 5. As the ECHO and ECG will be administered

Confidential Page 49 of 105

in a separate clinic than the pediatric neurology clinic, an asymptomatic subject receiving a second follow-up ECHO and ECG does not require a physical examination.

Subjects with positive findings on ECHO, ECG and/or physical examination should continue to be followed until the finding is resolved or stable and unlikely to change, with reports submitted as AEs to the ZX008 safety database.

If the subject completes the study (or discontinues from the study early) and is switching to commercially available drug, the subject will complete the EOS visit and follow the drug administration process outlined for commercial product as advised by the subject's physician. The EOS/ET and cardiac follow-up visits are not required.

Schedule of Post-Treatment Cardiac Follow-up Table 5.

The EOS/ET and card	liac follow-up visits are not requir	ed.
Table 5. Sched	ule of Post-Treatment Cardiac F	Tollow-up
Parameter		Have had any clinically significant cardiac sign or symptom regardless of the time on study drug ^a
ECHO and ECG	Follow-up 6 months post-treatment ^b in UK: additional 12-month follow-up in Germany, France, Netherlands: additional 24-month follow-up	Follow-up 6-24 months post-treatment ^b , and every 6 months until resolved, or stable and unlikely to change

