8.5. Adverse Event Reporting

8.5.1. Adverse Events

At each clinical evaluation, the investigator (or delegate) will determine whether any AEs have occurred. Adverse events will be recorded in the AE page of the CRF. If known, the medical diagnosis of an AE should be recorded in preference to the listing of individual signs and symptoms. The investigator must follow up on the course of an AE until resolution or stabilization. If an AE is ongoing after the end of study visit, the AE will continue to be followed up until resolution or stabilization.

If, during the study period, a subject presents with a pre-existing condition that was not noted at the time of study entry, the condition should be retrospectively recorded in the Medical History section of the CRF.

For results disclosure on public registries (e.g ClinicalTrials.gov), treatment-emergent adverse events will be included.

Confidential Page 60 of 105

22 September 2022

8.6. **Serious Adverse Events Reporting**

This study will comply with all applicable regulatory requirements and adhere to the full authorization areof. requirements of ICH Topic E2A (Clinical Safety Data Management: Definitions and Standards for Expedited Reporting [1994]).

In the event of a SAE the investigator or delegate must:

All SAEs that occur during the course of the study, beginning at Visit 1, whether or not causally related to IMP must be reported immediately via telephone or email or EDC (within 24 hours of the investigator becoming aware of the event) to the Sponsor or the CRO Medical Monitor.

- 1. Enter all relevant information into SAE eCRF, via the EDC.
- 2. In the event that EDC is down or not accessable the site can send a paper SAE form to the Safety team within 24 hours of becoming aware of the SAE and then enter the SAE into the eCRF page once the EDC is back up and accessible.

Adverse events occurring in the period between the time the subject gave written informed consent and the first exposure to IMP that meet 1 or more of the seriousness criteria for AEs must be reported to the Sponsor and the CRO Medical Monitor in the same manner as other SAEs and will be included in the clinical study database.

Any SAE that occurs 15 days after the last dose of study drug or the last visit, whichever is later that is considered to be causally related to IMP must be reported immediately (ie, within 24 hours of the investigator becoming aware of the event) to the Sponsor and the CRO **Medical Monitor.**

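### Protocol 8.4 and 8.6 set different causality conditions for SAEs that start after the observation period, and 8.6 gives no deadline or route for those judged not related

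*Protocol*

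**What the plan says.** Protocol 8.4 has AE and SAE reporting start at Visit 1 and "finish 15 days after the last dose of study drug or the last visit, whichever is later". For an SAE that starts later, it requires a report to the Sponsor if "the event could in some way be associated with IMP", and adds "irrespective of whether or not it is considered by the investigator to be causally related to IMP". It refers to 8.6 for this.

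Protocol 8.6 has two relevant rules. During the study: "All SAEs that occur during the course of the study, beginning at Visit 1, whether or not causally related to IMP must be reported immediately". For the late period, the rule covers an SAE falling beyond the 15-day or last-visit limit, "whichever is later that is considered to be causally related to IMP must be reported immediately", meaning within 24 hours, to the Sponsor and the CRO Medical Monitor.

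Protocol 8.3 makes causality a two-way choice. Related requires, among other things, that the event "is definitive pharmacologically; cannot to be attributed to concurrent disease or other factors or medications", and expects a reasonable response when drug is withdrawn or reduced. Not Related is for events without a reasonable association with study drug. There is also a default: "If a causality assessment is not provided for an AE (including an SAE), that AE will be considered as related to IMP".

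**The concern.** The section that defines the late-SAE duty sets aside the investigator's causality view. The section it sends the site to for the procedure makes that view the condition. A site that goes straight to 8.6, as the SAE reporting section, would find no instruction for a late SAE that it has classed Not Related.

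What is at stake is completeness of late serious safety data in a study whose primary objective is long-term safety. Protocol 1.1 describes raised SUDEP incidence in Dravet syndrome and lists cardiac arrhythmia among its possible mechanisms. A late death of this kind is easily attributed to the epilepsy. The Sponsor would want to see such an event whatever the site's opinion, and 8.4 appears written for that purpose.

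There may also be an effect on the tables. SAP 9.13.2 puts no end date on treatment-emergent events, and SAP section 14 tabulates serious and fatal TEAEs by relationship. If late SAEs reach the clinical database mainly when judged related, the split by relationship would be tilted. The documents do not say whether SAEs reported after the observation period enter that database, so this remains conditional.

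**Working it through.** No formula applies. The two rules, side by side, for an SAE starting after the observation period:

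| | Protocol 8.4 | Protocol 8.6 |
|---|---|---|
| Condition | possible association with IMP | considered causally related |
| Investigator's causality view | disregarded | decisive |
| Recipient | Sponsor | Sponsor and CRO Medical Monitor |
| Deadline | none stated; refers to 8.6 | 24 hours |

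**Step 1: sort late SAEs by the two conditions.**
- No plausible association, judged Not Related: neither section requires a report.
- Plausible association, judged Related or causality left blank (8.3 default): both sections require it.
- Plausible association, judged Not Related: 8.4 requires it; the late-SAE sentence in 8.6 does not reach it.

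The third class is the gap.

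**Step 2: is the third class real?** If possible association and Related meant the same, it would be empty. Under 8.3 they do not. Related calls for pharmacological definiteness and no alternative explanation. Once drug has stopped, a new late SAE can hardly show a response to withdrawal. SAP 9.13 uses a wider meaning, counting probably and possibly related events as related. The 8.6 filter thus has no single meaning, and on the protocol's own definition it is narrow.

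**Step 3: how hard can a causality filter bite?** Protocol 1.5.1 reports for Study 1503 that 80/330 subjects (24.2%) had a treatment-emergent SAE and 8/330 (2.4%) had an SAE considered related. If the 8 are among the 80, 8/80 = 10% of subjects with an SAE had one judged related. This illustrates the filter on treatment, in another study. It does not estimate the gap here: late events may differ, and many of the remaining SAEs may have had no plausible association.

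**Step 4: which late events have another route?**
- 6.3: "the subject will visit the clinic 6 months after the last dose", with ECG, ECHO and AE recording. Positive findings go to the safety database as AEs, with no causality condition.
- 8.8: pulmonary hypertension, cardiac symptoms needing intervention, and valvulopathy found outside study monitoring go to the CRO Medical Monitor within 72 hours, with no causality condition. The section does not say whether the duty continues after the observation period.
- 8.9: covers follow-up of AEs already present and of ECHO signs already found, so it does not pick up a new late SAE.

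This leaves mainly non-cardiac late SAEs, and subjects with no cardiac follow-up visit because they moved to commercial drug or were lost.

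**Step 5: when does the late period start?** The last visit in 8.4 is not defined. Protocol 7.2.12 ends AE collection at the follow-up clinic visit, which could be Visit 8 (EOS/ET + 14 days). Visit 9 (6 months after last dose) also records AEs, and some countries add follow-up at 12 or 24 months. If the last visit is Visit 8, the months up to cardiac follow-up fall in the period where the rules differ. If it is the final cardiac visit, those months are covered by the in-study rule, which ignores causality.

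**The case against.** The best counter-argument is that 8.6 does not restrict reporting. It never says that related events alone are reportable. A site can obey both sections: 8.4 fixes what is reported, and 8.6 adds a 24-hour deadline and a second recipient for the related subset. That reading is available, so the two rules are not strictly opposite. It still leaves the remaining 8.4 events with no stated deadline or route in the section cited for it. The general EDC procedure in 8.6 is framed around SAEs during the study.

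It can also be said that few events are affected: 8.4 covers only plausibly associated events, Not Related means no reasonable association, and missing causality defaults to related. This limits the size but does not empty the class, because of the strict definition of Related.

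A reader might infer that late valvulopathy or pulmonary hypertension can go unreported. The documents do not support this as a general conclusion: 6.3 and 8.8 capture most cardiac findings without asking about causality, ECHOs are read centrally (8.9.1), and the cardiac visits may lie inside the observation period.

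A reader might also infer that spontaneous reports are the only source for subjects who move to commercial drug. Protocol 3.1 says they will have follow-up ECHOs on commercial supply, although outside the study visits.

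**Conclusion.** The inconsistency stands, in current text, and should be corrected. It concerns one class: SAEs starting after the observation period that could be associated with IMP but are classed Not Related. Protocol 8.4 requires them; a site following 8.6 can omit them. It would overstate the point to count every late SAE not called related, since 8.4 does not ask for those without a plausible link.

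The number of events cannot be derived from the documents. It is probably small, and mainly non-cardiac or in subjects without cardiac follow-up. This rests on two assumptions: that some sites work from 8.6 alone, and that investigators apply the 8.3 definition of Related as written. The gap narrows if the last visit is the final cardiac follow-up, or if sites use the broader meaning in SAP 9.13.

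**What to change.** Use one late-SAE trigger in both sections. In 8.6, replace the causality condition in the late-SAE sentence with the 8.4 condition (possible association with IMP, whatever the investigator's causality judgement), keeping the 24-hour deadline and the recipients already named there, the Sponsor and the CRO Medical Monitor. In 8.4, state whether the last visit means Visit 8 or the last cardiac follow-up visit, so that all sites close the observation period at the same point.

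This takes one or two sentences in the next amendment and brings the late rule closer to the in-study rule in 8.6, which already ignores causality. The downside is a few more late SAE reports for sites and the Sponsor to process.
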